2.3.2 Secondary Endpoints

- The size of the tumor will be determined and net ΔTumor measurements used to determine the response.
- The safety of this window intervention will be reported descriptively, including tabulation
 of toxicities according to NCI CTCAE v.4, surgical complications, and length of hospital
 stay.
- The Ki-67 proliferative index will be measured in baseline and post-treatment tumor tissue as described, and will serve as a secondary endpoint (pharmacodynamic efficacy).²¹ The five prioritized biomarkers will be analyzed for correlations with ΔTumor size, as above. In addition, they will be analyzed for correlations with ΔKi-67.
- Non-prioritized biomarkers will also be evaluated for correlations with ΔTumor size and ΔKi-67. In order to assess biomarker response to ruxolitinib, we will test each component of the biomarker panel for within-patient differences between the pretreatment and post-treatment biospecimens (tumor tissue and blood) and compute the pvalues for each paired test (either a paired t test or the signed rank test). We anticipate a panel of 15 20 proteins will be tested for short-term modulation with TMAs. P values from paired data will be adjusted to control the expected false discovery rate by the method of Benjamini and Hochberg. Additional analyses of secondary endpoints will be conducted on an exploratory and hypothesis-generating bases using available material. These endpoints may include qualitative and semi-quantitative scoring of IHC in tissue arrays, gene microarrays and serum protein measures.

3 Study Design

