- 11. Concomitant Medications, any of the following should be considered for exclusion: Strong CYP3A4 inhibitors: (Patients must discontinue drug 7 days prior to starting ruxolitinib), including but not limited to boceprevir, clarithromycin, conivaptam, indinavir, itraconazole, ketoconazole, lopinavir, mibefradil, nefazodone, nelfinavir, posaconazole, ritonavir, saquinavir, telaprevir, telithromycin, or voriconazole. In addition, patients will be instructed to avoid grapefruit or grapefruit juice, starfruit, or Seville oranges.
- 12. Prisoners or participants who are compulsorily detained (involuntarily incarcerated) for treatment of either a psychiatric or physical (e.g., infectious) illness.

3.4 **Duration of Therapy**

In the absence of treatment delays due to adverse events, treatment will only be during the preoperative window of 14-21 days or up to 28 days for delays in planned surgery or until:

- Progressive disease at any time
- Any clinical adverse event, laboratory abnormality or intercurrent illness which, in the
 opinion of the Investigator, indicates that continued treatment with study therapy is not in
 the best interest of the participant
- Excessive toxicity
- Withdrawal of informed consent (participant's decision to withdraw for any reason)
- Pregnancy
 - All women of childbearing potential should be instructed to contact the Investigator immediately if they suspect they might be pregnant (e.g., missed or late menstrual period) at any time during study participation.
 - The Investigator must immediately notify Incyte in the event of a confirmed pregnancy in a patient participating in the study.
 - Study Closure or termination
 - Noncompliance

3.5 **Duration of Follow Up**

Patients will be followed for up to 12 weeks post-operation, as deemed clinically necessary or removal from study, or until death, whichever occurs first. Patients removed from study for unacceptable treatment related adverse event(s) will be followed until resolution or stabilization of all treatment related adverse events to Grade 2 or lower.

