- If participants experience any grade 3-4 ruxolitinib-related non-hematologic toxicities in the neo-adjuvant window, the study drug will be discontinued and they will be removed from the study. (Exception: Patients with asymptomatic grade 3 electrolyte abnormalities manageable with repletion) Patients may also be removed from study for intolerable non-hematologic toxicities of any grade, which persist despite optimal medical management.
- If participants experience grade ≥ 3 thrombocytopenia or neutropenia, ruxolitinib will be discontinued and they will be removed from the study.
- Grade 3 anemia does not require discontinuation from protocol. Patients may be transfused per discretion of the treating physicians.
- For mild or moderate (grade 1 or 2) side effects that are difficult to tolerate, treatment
 may be held for up to 1 week. Treatment may be resumed at the same dose, if there is
 improvement by at least one grade. Dose delays more than 1 week will not be permitted.
 If treatment is restarted, study physicians should aim for at least 3 days of ruxolitinib
 exposure prior to planned surgery.

In two Phase 3 clinical studies of ruxolitinib in myelofibrosis, the median time to onset of first CTCAE grade two or higher anemia was 6 weeks, and approximately 8 weeks until onset of grade 3 or 4 thrombocytopenia. In nearly all cases, ruxolitinib-induced anemia and thrombocytopenia could be reversed with dose reduction or interruption; occasionally red blood cell or platelet transfusions were required. Thus, given the short 2-3 weeks of treatment during this study, it is expected that few, if any, participants will develop hematologic abnormalities. Moreover, participants in the current study do not have a primary bone marrow malignancy which is the target of ruxolitinib and thus predisposes to hematologic toxicity. Any participants that experience anemia or thrombocytopenia may be transfused if deemed necessary by the treating physician.

Although clinically significant hematologic and non-hematologic toxicity is unexpected during the 14-21 days of protocol treatment in patients with operable HNSCC, a continuous monitoring rule for excess toxicity will be instituted. Please see Section 5.6 below.

5.6 **Monitoring and Toxicity Management**

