- e. Within 6 weeks of study entry (within 4 weeks preferred), and again within 5 days prior to planned surgery, patients will undergo cross-sectional radiological evaluation using diagnostic contrasted CT, PET/CT (with diagnostic contrasted CT), or MRI of regions with radiologically or clinically identifiable tumor. The minimum cross-sectional evaluation is a diagnostic, contrasted computed tomography (CT) scan of the neck. PET/CT is the preferred modality, **provided it includes a diagnostic, contrasted CT scan of the neck** however is not mandatory. For patients with severe allergy to iodinated contrast dye despite premedication, or in the case of physician preference, neck MRI may be substituted. The pre- and post-treatment imaging modality should be the same, i.e. if MRI was used at study entry, it should be used at the post-treatment, pre-surgical assessment. **NOTE**: in the event that a patient lacks a CT-measurable primary tumor or metastatic lymph node, measurable disease may also be established by caliper measurement of an oral cavity or oropharyngeal tumor (≥ 1 centimeter). In this case, caliper measurement should be repeated within 5 days prior to planned surgery.
- f. The first day of ruxolitinib treatment will be considered Day 1. Ruxolitinib will be administered at 20 mg po bid, for 1421 days, and will be discontinued on the day of surgical resection (following the morning dose). If surgery is delayed, the study drug may be continued until surgery, for a maximum of 28 days. The interval between the last dose of ruxolitinib and surgery will be 2-24 hours.
- g. Surgery will be scheduled during days 14-21 of ruxolitinib treatment. For logistical reasons, surgery may be delayed by up to 7 days. Postoperative complications, hospital days, and ICU days will be noted for each patient.
- h. Research blood samples will be obtained at screening and within the 5 days prior to scheduled surgery. One (1) purple top EDTA tube will be collected at each time point. Please refer to the laboratory SOPs for processing instructions.
- i. Archival tissue if available. If no archival tissue is available participants must undergo tissue biopsy at baseline. Research biopsies obtained at screening during planned surgery for resection of the tumor will be divided into fresh, fresh-frozen and paraffin specimens.

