7.5 Follow-up of Adverse Events

All adverse events will be followed with appropriate medical management until resolved. Patients removed from study for unacceptable adverse events will be followed until resolution or stabilization of the adverse event. For selected adverse events for which administration of the investigational drug was stopped, a re-challenge of the participant with the investigational drug may be conducted if considered both safe and ethical by the Investigator.

Follow-up Reports:

Additional information may be added to a previously submitted report by adding to the original MedWatch 3500 report and submitting it as follow-up or creating supplemental summary information and submitting it as follow-up with the original MedWatch 3500 form.

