8.2.2 Replacement Policy

Because this is an open label study with limited number of patients, 23 accrued eligible patients with clinical tumor assessments and biomarkers measurements at baseline and the end of study window are required for the study. Additional patients will be enrolled to replace patients without clinical tumor assessments and completed biomarker measurements for both time points at least one of the five biomarkers of interest. However, all patients will be followed and included for safety assessments.

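### Section 3.5 ends follow-up at removal from study, but footnote g and 8.2.2 expect surgical-safety data on every patient, so collection after removal for toxicity is unsettled

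*Combined protocol and SAP*

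**What the plan says.** **End of follow-up.** Section 3.5: "Patients will be followed for up to 12 weeks post-operation, as deemed clinically necessary or removal from study, or until death, whichever occurs first". Its next sentence adds that patients removed for unacceptable treatment-related adverse events "will be followed until resolution or stabilization of all treatment related adverse events to Grade 2 or lower".

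**Removal for toxicity.** Under 5.5, after a ruxolitinib-related grade 3-4 non-hematologic toxicity "the study drug will be discontinued and they will be removed from the study". Asymptomatic grade 3 electrolyte abnormalities that can be repleted are excepted. The same consequence follows grade 3 or worse thrombocytopenia or neutropenia; grade 3 anemia does not lead to removal. Section 8.2.3 describes the monitored group in the same terms: they stop drug and come off study.

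**Adverse-event follow-up.** Section 7.5: "Patients removed from study for unacceptable adverse events will be followed until resolution or stabilization of the adverse event".

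**What the safety endpoint needs.** Section 2.3.2 lists toxicities, "surgical complications, and length of hospital" stay, reported descriptively. Footnote g of the Study Calendar (6.1): "Postoperative complications, hospital days, and ICU days will be noted for each patient". Section 8.2.2, on replaced patients: "However, all patients will be followed and included for safety assessments".

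**The concern.** For the toxicity categories in 5.5, stopping drug and leaving the study happen together. These patients still face surgery, because a planned resection is an entry requirement (3.3.1) and the primary curative treatment (3.3). Their operative course is part of the safety endpoint, yet the section that governs follow-up duration gives a reason to stop collecting it.

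Patients with a recent drug-related cytopenia or other severe toxicity are the ones in whom an effect of pre-operative ruxolitinib on surgery would most plausibly show. If sites resolve the conflict in favour of 3.5, complications and hospital stay go missing selectively, by tolerability. In a multicenter study they could also go missing by site. Sections 7.2 and 8.5 raise a separate question, because they define the safety analysis set differently (at least one dose against at least 14 days of drug). Settling that question would not recover data that were never collected.

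**Working it through.** **Step 1: read the sections together for one hypothetical patient.** The patient stops drug and is removed on day 10 with grade 3 thrombocytopenia. The count has recovered by day 17 with no other treatment-related event open, and surgery is on day 20.

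- 3.5, first sentence: follow-up ends at removal, day 10.
- 3.5, second sentence, and 7.5: adverse-event follow-up continues to about day 17, three days before surgery. Neither mentions operative outcomes.
- 3.5.1: a discontinuing patient is to be seen if possible. Deaths within 30 days of the last dose must be reported, so to about day 10 + 30 = 40. Nothing is said about non-fatal surgical outcomes.
- Footnote g: complications, hospital days and ICU days are recorded. The footnote opens by placing surgery within the treatment days, so its reach to a patient already off drug and off study is not explicit.
- 8.2.2: the patient is followed and included for safety.

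The first three items give no basis for recording a non-fatal complication or the length of stay. The last two do. The documents do not say which prevails.

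**Step 2: size of the group.** The inputs come from 5.2 and 3.2: a Beta(1, 9) prior for treatment-related discontinuation, a 33% bound, and 45 patients.

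The plan's own figures reproduce first. With r stops in n patients, the posterior is Beta(1 + r, 9 + n − r).

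- 5 of 6: Beta(6, 10) gives P(rate > 0.33) = .629, and the binomial tail at 0.33 is .017.
- 14 of 33: Beta(15, 28) gives .590, with tail .167.

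All ten rows of Table 5.2 agree to three decimals in both columns.

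- Prior mean: 1/(1 + 9) = 10%, and 0.10 × 45 = 4.5 patients.
- At the bound: 0.33 × 45 = 14.85, about 15 patients.
- Stops possible at a listed boundary without triggering the rule: one fewer than the tabulated count, so up to 4 of 6, 10 of 23 or 13 of 33.

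These counts are upper limits for missing operative data. A patient whose treatment-related event is still open at surgery remains under follow-up, and a site that applies footnote g will record the outcome anyway.

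**Step 3: possible effect on the reported complication rate.** The documents give no complication rates, so those below are assumptions. Let a be the rate in patients not removed, b the rate in removed patients, and d the share removed. If all removed patients are missing, the report shows a, the all-treated rate is (1 − d)a + db, and the understatement is d(b − a).

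| d | a | b | All-treated rate | Understatement (points) |
|---|---|---|---|---|
| 10% | 20% | 20% | 20.0% | 0 |
| 10% | 20% | 40% | 22.0% | 2.0 |
| 10% | 20% | 60% | 24.0% | 4.0 |
| 33% | 20% | 20% | 20.0% | 0 |
| 33% | 20% | 40% | 26.6% | 6.6 |
| 33% | 20% | 60% | 33.2% | 13.2 |

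**The case against.** The strongest reply is that the protocol already orders the collection. Footnote g covers each patient, 8.2.2 says all patients are followed for safety, and 5.6 and 7.1.1 make every treated patient evaluable for safety. A reader might infer from 3.5 and 5.5 alone that surgical outcomes will be collected mainly in patients who tolerated the drug, and that the reported rate will be biased downward. The documents do not support that. They contain instructions in both directions, so the loss is a risk rather than a settled result. The direction of bias also depends on complication rates that the plan does not give.

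Three narrower objections also stand.

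- A reader might infer that every stop of drug ends participation. Section 3.4 lists reasons for ending treatment without saying so, and 3.5.1 keeps some discontinued patients evaluable. The link holds for the toxicity removals in 5.5.
- A reader might see a serious clash between 3.5 and the general sentence of 7.5, "All adverse events will be followed with appropriate medical management until resolved". The next sentence of 7.5 deals with removed patients in nearly the same terms as 3.5. What remains is that 3.5 has a grade threshold and a limit to treatment-related events, and 7.5 has neither.
- Sections 4.1.1 and 5.5 expect little clinically significant toxicity in a 2-3 week exposure, and surgical safety is a descriptive secondary endpoint in a biomarker study. The affected group may be very small.

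None of this tells a site which section to follow after removing a patient for toxicity before surgery.

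**Conclusion.** The point holds as an internal conflict. Sections 3.5 and 5.5, read as written, allow operative data collection to end before surgery in patients removed for drug toxicity, whereas footnote g and 8.2.2 require it. The adverse-event extension does not close the gap, because it can expire before surgery and does not cover complications or length of stay. Deaths within 30 days of the last dose are still captured.

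At most about 4-5 of 45 patients are affected at the 10% prior mean, and about 15 at the 33% bound. Both counts assume that all 45 are treated and that every toxicity removal loses its operative data. Under the assumed complication rates above, the understatement runs from 0 to 4 points at 10% removal and from 0 to 13.2 points at 33%. It should be corrected, because the group at risk is selected by toxicity and the remedy is cheap. It does not touch the primary biomarker analysis.

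**What to change.** Reconcile 3.5, 3.5.1 and 5.5 with footnote g and 8.2.2 by defining two separate states for data collection: *discontinued study drug* and *withdrawn from study*. State that any patient who took at least one dose and has not withdrawn consent stays in data collection through surgery and the 4- and 12-week post-operative visits, including complications, hospital days and ICU days. Removal for toxicity under 5.5 should then no longer end follow-up under 3.5.

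The cost is a short amendment and a few extra CRF pages for early stoppers; the protocol already describes both post-operative visits as standard. No dosing, stopping or other treatment rule changes. As a minor tidy-up, use one event-closure wording in 3.5 and 7.5.

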3.5.1 Procedures for discontinuation

Participants who discontinue should, if possible, be seen and assessed by an investigator(s). The reason for withdrawal and the date of withdrawal must be documented. If possible, any diary cards and investigational products should be returned by the participant as soon as possible after study discontinuation. If patient had screening tissue samples obtained, has taken at least 14 days of drug, and has undergone response assessment, they are evaluable.

If the reason for withdrawal from the trial is the death of the participant, the two options for categorizing withdrawal are either disease recurrence or an adverse event (AE; more than one

Phase 2 - Ruxolitinib Page 27 of 67

AE may be documented as a reason for withdrawal). Only one event will be captured as the cause of death.

Note: death is an outcome and not an AE. All deaths that occur within the trial period or within 30 days after administration of the last dose of trial drug must be reported to Incyte primarily for the purposes of serious adverse event (SAE) reporting; however, deaths due unequivocally to progression are not SAEs.

3.6 Study Timeline

3.6.1 Primary Completion

The study will reach primary completion 24 months from the time the study opens to accrual.

3.6.2 Study Completion

The study will reach completion 36 months from the time the study opens to accrual.

4 Study Drugs

4.1 Description, Supply and Storage of Investigational Drugs

4.1.1 Ruxolitinib (JAKAFI®, INCB018424)

Ruxolitinib is dosed orally, every morning and every evening, and can be administered with or without food. If a dose is missed, the patient should not take an additional dose, but should take the next scheduled prescribed dose. In the case of emesis, the patient should not take an additional dose, but should take the next scheduled prescribed dose. For patients unable to ingest tablets, ruxolitinib can be administered through a nasogastric or percutaneous gastrostomy tube (8 French or greater) as follows:

- Suspend three or four 5 mg tablets (dose dependent according to platelet count, as described under "Study drug treatment" in section 5.2) in approximately 40 mL of water with stirring for approximately 10 minutes.
- Within 6 hours after the tablets have dispersed, the suspension can be administered through the feeding tube using an appropriate syringe.

The tube should be rinsed with approximately 75 mL of water. The effect of tube feeding preparations on ruxolitinib exposure during administration through a nasogastric tube has not been evaluated.

Participants will be asked to indicate on a drug diary (see Appendix 4) when doses of study drug are taken in order to monitor for compliance. Participants may also use the drug diary for notations on side effects and other treatment related events. The Investigational Pharmacy will maintain a drug accountability log to record ruxolitinib received, dispensed and/or destroyed. Unused drugs will be destroyed locally and will not be returned.

NOTE: for current information, please see the most recent version of the Investigator Brochure

Classification

Phase 2 - Ruxolitinib Page 28 of 67

Ruxolitinib is a Class I molecule under the Biopharmaceutical Classification System, with high permeability, high solubility and rapid dissolution characteristics. In clinical studies, ruxolitinib is rapidly absorbed after oral administration with maximal plasma concentration (C_{max}) achieved approximately 1 hour post-dose

Mechanism of Action

Ruxolitinib (INCB018424 phosphate, INC424, ruxolitinib phosphate) represents a novel, potent, and selective inhibitor of JAK1 (Janus kinase 1) (inhibition concentration 50% [IC50]=3.3 \pm 1.2 nM) and JAK2 (IC50=2.8 \pm 1.2 nM) with modest to marked selectivity against TYK2 (tyrosine kinase 2) (IC50=19 \pm 3.2 nM) and JAK3 (IC50=428 \pm 243 nM), respectively. Ruxolitinib interferes with the signaling of a number of cytokines and growth factors that are important for hematopoiesis and immune function.

Metabolism

Ruxolitinib was eliminated predominantly by oxidative metabolism (leading to hydroxylated metabolites M7, M8, M14 and M18 and keto metabolites M14 and M18 (Figure 4-1), followed in some cases by limited subsequent glucuronidation in humans and animal species

Contraindications

Hypersensitivity to the active substance or any of the excipients.

Potential Drug-Drug Interactions

Ruxolitinib is primarily protein bound (97%) and is metabolized by CYP3A4 in the liver. Significant drug-drug interaction may occur when ruxolitinib is administered with inducers or inhibitors of CYP3A4. Concomitant administration of ruxolitinib with strong inhibitors of CYP3A4 such as ketoconazole may lead to significant increases in C_{max}, AUC, and half-life, thus such patients should not be included on study. No dose adjustment is recommended when ruxolitinib is administered with mild inhibitors or inducers of CYP3A4, although these patients should be carefully monitored. Grapefruit juice is also a potent CYP3A4 inhibitor, thus the consumption of grapefruit juice should be avoided during ruxolitinib treatment.

Warnings and Precautions

Based on clinical experience to date in myelofibrosis, the following adverse effects may be associated with ruxolitinib: thrombocytopenia, anemia, neutropenia, bruising dizziness, headache, urinary tract infection, weight gain, flatulence, and herpes zoster. Thrombocytopenia, anemia, and neutropenia are dose-related effects, which occur at a median of 8 weeks after initiation of ruxolitinib, and in studies of longer duration have been generally treated by withholding ruxolitinib. Occasionally patients with anemia may require a transfusion. Patients taking ruxolitinib may be at risk for infection and should be monitored for this. The incidence of clinically significant hematologic toxicity is expected to be very low in the current study population, due to the short ruxolitinib exposure, as well as the absence of a primary bone marrow malignancy predisposing to hematologic toxicity.

Some people who take ruxolitinib have developed certain types of non-melanoma skin cancers.

Availability

All tablets are oval and white with "INCY" on one side and "25" on the other. Additional information regarding ruxolitinib can be found in the package insert.

Storage and handling

Phase 2 - Ruxolitinib Page 29 of 67

In addition to the active ingredient, each ruxolitinib tablet contains microcrystalline cellulose, lactose monohydrate, magnesium stearate, colloidal silicone dioxide, sodium starch glycolate, povidone, and hydroxypropyl cellulose. Ruxolitinib will be supplied as 5 mg tablets in bottles containing 60 tablets each. Labels contain, at a minimum, the following information: product name, tablet strength, batch number, directions for use, storage conditions, and appropriate caution statements. Ruxolitinib tablets should be stored in a secure area at 25°C (77°F); excursions permitted between 15°-30°C (59°-86°F).

Side Effects

Complete and updated adverse event information is available in the Investigational Drug Brochure and/or product package insert.

4.2 **Drug Accountability**

The Investigational Pharmacist will manage drug accountability records. Damaged supplies will be destroyed at the study site and adequate records of the damaged supplies will be kept at the site. Study investigators will be responsible for drug accountability.

4.3 **Drug Ordering**

Ruxolitinib will be supplied by Incyte Pharmaceuticals.

